## **Recruitment of Subjects.**

Subjects will be recruited through radio ads and flyers distributed throughout the community. The advertisements will direct potential participants to sign up either through our website (utdengage.com) or via phone.

For website signup: Participants will complete an initial screening form. Research staff will follow up with all participants within 48 hours/2 business days – for those who are not eligible based on the screening, an email will be sent to participants informing them as such. For those participants who may be eligible based on the initial screening, they will receive a phone call from a member of research staff with a second brief screening questionnaire for eligibility (the Telephone Interview for Cognitive Status (TICS)), as well as provided with upcoming dates for informational meetings. They will also be invited to fill out the enrollment form online or via email.

For phone signup: Participants will call in and receive the initial screening form over the phone. For those who are deemed ineligible based on this screening, participants will be informed immediately. For those who may be eligible, research staff will inform participants that they will receive a second phonecall within 48 hours/2 business days for a potential second screening. At this second screening, participants will be administered the TICS screening, and be given information about upcoming informational meetings. They will also be invited to fill out the enrollment form, either online or via email. Interested individuals will attend the informational meetings and learn about the logistics of the study, the time commitment, randomization of group assignment, compensation and criteria for potential participants, as well the minimal risks associated with each condition. These meetings are meant to educate a potential pool of participants who, after the meeting, may be screened and eligible to be enrolled in the study. The sustained nature of the commitment to the project will be explained to subjects. Those volunteers who meet the inclusion/exclusion criteria and are interested in participation after learning more will be provided with a detailed consent form by trained laboratory personnel. Written consent will be obtained. Additionally, individuals who participate in the behavioral portion of this study will also be screened for the MRI portion of the study. If subjects meet the MRI criteria, they may be invited to participate in an fMRI session, in addition to the behavioral component for which they have already qualified.

## **Potential Risks.**

Behavioral Testing. There is minimal risk associated with the cognitive/psychosocial tests, but subjects may feel emotionally distressed if they perceive their performance is not satisfactory.

Intervention. Subjects in the interventions will experience risks that are no more than a person is faced with on a daily basis, and subjects are monitored at all times. There is also the risk of lower affect and disappointment as the engagement manipulation ends.

MRI. MRI scanning involves the use of magnetic and radio frequency energy. Therefore, participants with the following metal permanently attached to or with their bodies will not be allowed to participate in the MRI session: permanent eyeliner or eyebrows; heart pacemaker, heart valve replacement, or aortic clips; metal fragments in the eyes, skin, or elsewhere in the body; brain clips or pieces of metal used in aneurysm surgery or intercranial bypass; venous umbrella; pieces of metal in the body resulting from work as a sheet-metal worker or welder; clips placed in an internal organ; prosthetic devices, such as middle ear, eye, joint, or penile implants; joint replacement; hearing aid that cannot be removed; neurostimulator; insulin pump; intrauterine device (IUD); shunts or stents; metal mesh or coil implants; metal plate, pin, screws, or wires, or any other metal implants. The technologist and investigators will screen the participants for such contraindicators.

Because of the strong magnetic field associated with the scanner, it is rare, but possible, that a metallic object could fly through the air toward the scanner and hit the subject. To reduce this risk, everyone in the vicinity of the magnet will remove all metal from their clothing or pockets.

There are no known risks or adverse effects resulting directly from exposure to magnetic fields and radio frequency energy used in this study. Some people experience nervousness from confinement in a tight space (claustrophobia). Also, the MR scanner produces tapping sounds during operation, which may reach very loud levels. To minimize any discomfort from this noise, the patient will be provided with disposable earplugs and headphones that suppress external noise levels but do not eliminate voice communication with the scanner operator. If the participant is unable to tolerate being in the scanner, we will stop the scan immediately.

Other risks of MRI, but that rarely occur: 1) Neurostimulation. In some cases, it is possible that the subject might experience neurostimulation effects, such as muscle twitches and tingling sensations, due to the rapid switching of

magnetic field gradients used in these examinations. There are no known risks associated with these effects; 2) Quench Hazard. The MR scanner uses liquid nitrogen and liquid helium. It is possible that the liquid nitrogen and helium will boil off rapidly and fill the magnet room with extremely cold dense gaseous nitrogen and helium, which can be dangerous if breathed for more than a few moments. The scanner operator will obviously detect this and immediately provide assistance to anyone inside the magnet room.

Although there is no evidence of any risk to pregnant women, we will exclude women who are pregnant or suspect they may be pregnant. Pregnancy is an exclusion.

We anticipate that the results of these studies will help in the overall understanding of cognitive function and may lead to improved treatment modalities for patients with cognitive deficits. The potential benefits anticipated in improved treatment and management of patients with memory disorders are expected to far outweigh the minimal risks associated with these studies. MRI examinations are generally considered non-invasive and the risks involved in this study are no more than the MRI scans routinely employed in clinical practice. Therefore, the risks of this study are minimal.

Special Precautions. The risks associated with specific study procedures will be thoroughly explained to participants. Written informed consent will be required before each session. To minimize the risk of anxiety during MR scans, participants will be in the scanner for a maximum of 90 minutes per session. We will make it clear to participants that they can stop the study and exit the scanner at any time. Participants will be checked multiple times for metal or other devices that could pose a danger in the MR environment. Also, participants will be given hearing protection during scanning. Reassurance will be provided as needed and they will be reminded that their continued participation in the study is completely voluntary.

### **Subject Safety and Data Monitoring.**

To ensure study integrity and to reduce any risk to participants, study personnel will closely monitor: (1) the participant's study experience, (2) the actual versus target accrual rates, (3) participant attrition (e.g. withdrawals, dropouts), (4) patterns of adverse events and unanticipated events, (5) patterns of protocol deviations and violations, (6) study stopping points, and (7) changes in risks and benefits. Potential risks and discomforts will be prevented and/or minimized to the greatest extent possible using procedures such as the appropriate training of personnel, monitoring of personnel, withdrawal of subject upon evidence of difficulty or adverse event, and referral of participants for treatment, counseling, or other necessary follow-up in accordance to the guidelines mentioned above. The study records will be treated as private as the extent permitted by law. Reassurance will be provided as needed, and participants will be reminded that their continued participation in the study is completely voluntary.

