We propose a study that would allow us to evaluate the effectiveness of engagement on cognitive function and determine whether mental effort is a contributing factor to changes in cognitive function. We plan to enroll 90 participants in the Impact of Challenging Engagement study and assign them to one of three groups: high-demand photography, moderate-demand photography, and active placebo. These initial groups will allow us to collect data and address the feasibility for converting the project into a full trial. Participants will engage in their different engagement conditions for 15 hours per week, based on successful results from the initial AIM study. In the Impact of Challenging Engagement study, we expect to expand on the results of the AIM study to determine if high-demand activities result in any observable brain changes when compared to moderate demand or placebo activities. Behavioral and neural measures of cognitive change will be assessed, providing considerable insight into mechanisms of change. Subjects will be characterized thoroughly in terms of behavioral tests of cognitive function, and a subset of subjects who meet neuroimaging criteria will undergo an fMRI procedure.

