### **Concise Summary of Project.**

In the proposed research, we will enroll a total of 90 subjects over 16 weeks. Just as in the original AIM study (approved by UTSW IRB #072010-144), subjects will be randomly assigned to participate in one of 3 conditions with 30 subjects per group. Two of the groups involve active intellectual engagement. In these groups, novice subjects will engage in high-demand or moderate-demand photography in five hours of structured courses with professional instructors for each of the 16 weeks. Subjects will also be required to put in an additional investment of 10 hours each working on a project to which they can apply their learned skills. Subjects are expected to be working on their projects for a total of 210 hours of engagement over the 16 weeks. We will measure pre/post change in multiple measures of cognitive and neural function, affect, and activity over the 16 weeks, and contrast change with one control group. The control group, the Placebo Control, will engage alone at home in tasks that are relatively low in intellectual engagement such as listening to music and radio or completing work-books that rely primarily on activation of knowledge. Preliminary data collected at the University of Illinois has indicated that volunteers willingly engage in a similar program.

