### **Intervention (Weeks 3-16)**

Subjects will be pseudo-randomly assigned to intervention groups (based on gender and education criteria and the needs of the study) and then will participate for at most 14 weeks in the manipulation to which they were assigned. All will be told that there are numerous studies in the literature suggesting that the condition to which they were assigned is a form of engagement that has been shown to improve cognition. This is true, as many correlational studies have shown that engagement in tasks as passive as watching television is related to better cognition. All subjects will be required to agree to participate in any of the three conditions so that no condition will be biased. They will be novices at the use of the digital camera and will have had only minimal experience with computers, , or digital photography. Subjects who use traditional cameras will be permitted to enroll.

**Productive Engagement Groups.** (High-Demand and Moderate-Demand Photography) Sixty total participants will be assigned to one of the productive engagement groups (with thirty participants in each group): high-demand photography, and moderate-demand photography. Before the intervention begins, subjects will be provided equipment appropriate to their intervention for them to loan throughout the 12- to 14-week intervention. Participants in either of the photography groups will be supplied digital cameras. These 30 participants in each group may be separated further into smaller sections based on instructor availability in order to take advantage of smaller class sizes.

Each group will meet for 2.5 hours twice a week (5 hours per week total) at the research site. During this time, subjects will be stepped through a detailed curriculum by professional instructors, and those who learn techniques quickly will be pushed along so that maximum new learning occurs for each subject. Additionally, all subjects will be required to spend an additional 10 hours working on a special project at the research site without any formal instruction. This project is meant to provide participants with an opportunity to apply their skills to a task as they are learning. The high-demand photography group will learn similar skills as the moderate-demand photography group, but will learn them at a significantly quicker pace and, therefore, will learn more skills by the end of the intervention than the moderate-demand group.

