### **Post-Intervention Test (Weeks 15-16)**

In the final two-weeks, participants will repeat their cognitive testing and take-home questionnaires. In addition, if they had an MRI session at pre-test, subjects will be asked to repeat the neuroimaging portion of the study as well.

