### Analyses of Secondary Outcomes.

*Dose-response.* We anticipate that there will be a dose-response relationship, with the control arms having the lowest values, high-engagement arms, the highest values, and moderate-engagement arms having values in between. We will construct mixed models to estimate the sizes of these effects, and to determine whether effects are linear or nonlinear in the degree of engagement.

*Subgroup Analyses.* We will conduct a number of analyses aimed at estimating treatment effects within strata of age (younger or older than age 72), gender (male or female), education (greater or less than 14 years), and center (Dallas or Hamburg). We expect each of these strata to comprise roughly half of the subjects, except that our sample will likely be 65% female, reflecting the sex imbalance in the elderly. We will replicate our main analyses in each of the stratum subgroups, and additionally test for interactions.

*Incomplete data.* A major concern in any follow-up study is that there will be substantial dropout, eroding trial power. As indicated above, we expect no more than 15% to 20% of subjects to fail to complete the followup evaluation schedule. This is not a large fraction of dropout, and we have provided for its effects on power in our sample-size calculations. A second concern is that dropouts may differ systematically from completers, potentially introducing bias into estimated treatment contrasts. Our primary approach to analysis is to use mixed models, which give correct results as long as the dropout mechanism is missing at random — i.e., the probability of dropout, given the potentially missing observation and all prior observed data, does not depend on the potentially missing observation. Moreover, as long as the dropout is roughly balanced between treatment arms, it is unlikely to have a substantial biasing effect on estimated treatment effects, even if the dropout mechanism is not missing at random. In any event, if dropout is excessive or is unbalanced between arms, or there is concern that it is not missing at random, we are prepared to conduct analyses for sensitivity to nonignorable (i.e., biasing) dropout using general methods that [name] has developed.

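### Withdrawal for undefined difficulty, with no stated testing of those withdrawn, could lose outcomes unequally between arms that are built to differ in demand

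*Combined protocol and SAP*

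**What the plan says.** **The trigger.** Under Subject Safety and Data Monitoring, the protocol states: "Potential risks and discomforts will be prevented and/or minimized to the greatest extent possible using procedures such as" a list of examples, one of which is "withdrawal of subject upon evidence of difficulty or adverse event". The other examples are staff training, staff monitoring and referral for care. Difficulty is not defined, and no decision-maker is named. The same section says attrition will be monitored, but not that it will be broken down by arm or by reason.

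**The contrast between arms.** The Purpose section sets out to "determine whether mental effort is a contributing factor to changes in cognitive function". Under Intervention (Weeks 3-16), both photography groups cover similar skills, and the difference is in pace: high-demand participants "will learn them at a significantly quicker pace and, therefore, will learn more skills by the end of the intervention than the moderate-demand group". The Concise Summary describes the placebo tasks as low in intellectual engagement and done alone at home.

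**Contact with staff.** Photography participants have 5 class hours and 10 project hours a week at the research site. At-home participants visit the lab weekly.

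**Testing.** The Post-Intervention section says: "In the final two-weeks, participants will repeat their cognitive testing and take-home questionnaires". Neither this section nor the mid-intervention section (weeks 8-9) says whether withdrawn people are included.

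**Analysis.** The SAP's primary analysis is ANCOVA on baseline, with a mixed model offered as equivalent. Its paragraph on incomplete data relies on missing at random and argues that dropout of similar size in each arm is unlikely to bias the contrast. It offers sensitivity analyses if dropout is excessive, unbalanced or suspected not to be at random.

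**The concern.** The provision withdraws the subject, not only the activity, and its trigger is worded in terms close to the experimental variable. If staff apply it to people struggling with the course, it would be met more often where the course is harder. Between the two photography arms the difference would come from pace. Between photography and at-home it would come from demand and also from how much staff can observe.

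If those withdrawn are then not tested, the comparison becomes people who coped with high demand against a less selected group. Staff judgement of who is struggling is not a variable in any planned model. Someone withdrawn before weeks 8-9 contributes only a baseline score. Someone withdrawn later also contributes a mid-test score, which helps but may not carry all the information. With 30 per arm, a few lost outcomes matter.

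**Working it through.** **1. The plan's own figures.** The Concise Summary states that "subjects will be randomly assigned to participate in one of 3 conditions with 30 subjects per group", so 3 x 30 = 90. The documents give no alpha, power, effect size or SD, so 90 cannot be reproduced. The only dropout figure is overall and for all causes: "we expect no more than 15% to 20% of subjects to fail to complete the followup evaluation schedule". Applied evenly, that leaves 30 x 0.85 = 25.5 to 30 x 0.80 = 24 completers per arm.

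**2. Assumptions, none of them from the documents.**
- A fraction d of the high-demand arm is withdrawn and not tested, with d = 10% or 20% (3 or 6 of 30). No one is withdrawn from the comparison arm.
- Those withdrawn are the lowest on a struggling score that correlates rho = 0.3 or 0.5 with the outcome after adjustment for baseline.
- There is no true treatment effect.

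**3. Bias.** In residual SDs, the retained high-demand mean shifts by k = rho x phi(z_d)/(1 - d). Here z_d is the d-quantile of the standard normal and phi its density.
- d = 10%: phi = 0.1755, and 0.1755/0.90 = 0.195. So k = 0.06 (rho 0.3) or 0.10 (rho 0.5).
- d = 20%: phi = 0.27996, and 0.27996/0.80 = 0.34995. So k = 0.105 (rho 0.3) or 0.17 (rho 0.5).

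**4. Type I error, two-sided, nominal 5%.** SE = sqrt(1/30 + 1/(30(1 - d))), which is 0.265 at d = 10% and 0.274 at d = 20%. Error rate = 1 - Phi(1.96 - k/SE) + Phi(-1.96 - k/SE).
- d = 10%: 5.6% (rho 0.3) and 6.6% (rho 0.5).
- d = 20%: 6.7% (rho 0.3) and 9.8% (rho 0.5).

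**5. Simulation check.** ANCOVA, 30 per arm before withdrawal, 4,000 runs per setting, assumed baseline-to-post correlation 0.7.

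| Selection | Bias, residual SD | Rejection rate |
|---|---|---|
| High-demand only, d 10%, rho 0.3 | 0.05 | 4.6% |
| High-demand only, d 10%, rho 0.5 | 0.09 | 6.5% |
| High-demand only, d 20%, rho 0.3 | 0.10 | 6.8% |
| High-demand only, d 20%, rho 0.5 | 0.16 | 9.1% |
| High-demand only, struggling linked to baseline alone | 0.00 to 0.01 | about 5% |
| Same selection in both arms | within 0.005 of zero | 5% to 6% |

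The simulation agrees closely with the formula on bias. At the mildest setting it shows no inflation of the rejection rate.

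**6. Scale.** At an assumed two-sided 5% alpha and 80% power, the detectable effect is (1.96 + 0.84) x sqrt(2/n): 0.72 residual SD at n = 30 and 0.81 at n = 24. With correlation 0.7, one residual SD is sqrt(1 - 0.49) = 0.714 outcome SD. A bias of 0.05 to 0.17 residual SD is therefore about 0.04 to 0.12 outcome SD.

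**The case against.** A reader might infer that the protocol removes strugglers from the high-demand arm and so inflates its result. The documents do not support that, for four reasons.

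- **Meaning.** The phrase is one example in a sentence about risks and discomforts, is paired with adverse events, and applies to all arms. The Potential Risks section names distress over test performance, low affect as classes end, and scanner problems, but not slow learning. Difficulty may well mean distress or trouble tolerating testing or MRI. No section tells staff to withdraw slow learners, and the weekly instructor assessments carry no withdrawal rule. This stands. But the coursework reading is not excluded, and withdrawal over distress about performance could also relate to outcome.
- **Lost data.** Loss of outcomes is inferred from silence. The testing sections speak of participants and bar no one. This stands, but nothing secures the tests either.
- **Existing handling.** Attrition is monitored, and the SAP foresees sensitivity analyses for unbalanced dropout. This stands in part. Monitoring does not recover an outcome that was never measured. The SAP also does not say what counts as excessive or unbalanced, or set out the analysis for this trial.
- **Direction.** Bias needs unequal withdrawal, lost outcomes and a link between struggling and the baseline-adjusted outcome. If effort drives benefit, those who struggle could gain more, and the sign would reverse. This stands.

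**Conclusion.** The point holds in conditional form. An undefined withdrawal trigger, with no stated follow-up of those withdrawn, could cause loss of outcomes that differs by arm and relates to outcome. The planned baseline adjustment and missing-at-random models would not fully remove the resulting bias. The SAP's reassurance about balanced dropout is weakest in this case.

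Under the assumed 10-20% withdrawal from the high-demand arm only and correlations of 0.3-0.5, the bias is about 0.05-0.17 residual SD, with analytic type I error of about 5.6-9.8%. That is modest beside a detectable effect of roughly 0.7-0.8 residual SD. It is about zero if selection is the same in both arms or acts only through baseline. Selective removal from the high-demand arm, and a result tilted towards the study hypothesis, are possibilities and not facts in the documents. The case for acting is that the remedy is cheap, works under either meaning of difficulty, and cannot be applied once the tests have been missed.

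**What to change.** Leave the criterion for stopping to the sponsor and the investigator. In Subject Safety and Data Monitoring, and in the mid- and post-intervention testing sections, separate stopping the activity from leaving the study:

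- Invite everyone who stops the activity to the planned weeks 8-9 and weeks 15-16 tests, and to the second scan if eligible and safe, unless consent is withdrawn.
- Analyse them in the arm to which they were assigned.
- Record the reason for stopping (difficulty, adverse event or own choice) and report withdrawals by arm and reason. This also gives the SAP's contingent sensitivity analysis something to act on.

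**Cost.** A sentence or so in each section, and some staff effort to bring people back. Subject Compensation already sets $75 per completed cognitive session, so two remaining sessions cost 2 x $75 = $150 per person. For the 3 to 6 people in the assumed scenario that is $450 to $900. The set fees for post-test questionnaires ($50) and a second scan ($100) apply where these are completed.
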